### 9 SAFETY AND ADVERSE EVENTS

### 9.1 Definitions

The definitions for adverse event, adverse device effect, serious adverse event, serious adverse device effect, and unanticipated adverse device effect are provided below (ISO 14155:2011, 21 CFR 812.3(s)).

- Adverse Event (AE): an adverse event is any untoward medical occurrence in a subject which need not be related to the device under investigation.
- Adverse Device Effect (ADE): an adverse device effect is any untoward or unintended response to a medical device which may result from insufficiencies in the instructions for use or deployment of the device, or from use error.
- Serious Adverse Event (SAE): a serious adverse event is an adverse event that results in death, inpatient
  hospitalization, severe or permanent disability, a life threatening illness or injury, fetal distress, fetal death, a
  congenital abnormality, a birth defect, or medical or surgical intervention to prevent permanent impairment to body
  or structure.

- Serious Adverse Device Effect (SADE): a serious adverse device effect is an adverse device effect that results in death, inpatient hospitalization, severe or permanent disability or is life threatening.
- Unanticipated Adverse Device Effect (UADE): any serious adverse effect on health or safety or any life threatening
  problem or death cause by or associated with, a device, if the effect, problem, or death was not previously identified
  in nature, severity or degree of incidence in the investigational plan, or application (including a supplementary plan
  or application) or any other unanticipated serious problem associated with a device that related to the rights, safety
  or welfare of subjects. Refer to the Device Risk Analysis and Risk Assessment section for details on anticipated
  adverse device effects.

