#### 5.2 Inclusion Criteria

- Age greater than 18 years
- ASA physical status III or IV
- Scheduled for an elective surgical procedure requiring endotracheal intubation and the use of an arterial pressure monitoring catheter placed prior to induction of general anesthesia

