# 9.3 Adverse Event Reporting:

- All Adverse Events, both Anticipated and Unanticipated, must be recorded in the within the CRF and in the Adverse Event Report Form.
- All Adverse Events must be promptly reported to the Sponsor.
- All Unanticipated Adverse Device Effects will be also reported to both the Sponsor and the IRB.
- Both Serious Adverse Events and Unanticipated Adverse Device Effects must be reported to the Sponsor within 48 hours. All other Adverse Events should be reported to the Sponsor within 5 business days.
- All Serious Adverse Events will be also reported to the IRB per IRB reporting requirements. These reports may include, but will not be limited to: date of onset; brief description of the events; their treatment; whether they resulted in death, inpatient hospitalization, severe or permanent disability or were life threatening; their relationship to the study device; and resolution.

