#### 12 MONITORING PLAN

- 12.1 As the sponsor of this clinical investigation, Masimo Corporation is required by 21 CFR Part 812, of the Food and Drug Administration regulations to monitor and oversee the progress of the investigation. The monitor(s) assigned by Masimo Corporation to this task will be a direct employee from the Clinical Research department trained on departmental SOPs on conduct and monitoring of sponsored studies.
- 12.2 In accordance with good clinical practices guidelines, there will be at least three scheduled monitoring visits to ensure overall regulatory compliance of the study:
  - An initiation visit, prior to any subject enrollment to confirm site readiness, and to document training on the study protocol and procedures, and use of equipment.
  - At least one monitoring visit during enrollment, when about 10-15% done and/or every year
  - A final close out visit after the last patient had finished the study.
- 12.3 The monitor will contact and visit the investigator and will be allowed, on request, to have access to all source documents needed to verify the entries in the CRFs and other GCP-related documents (IRB approvals, IRB correspondences, and ICFs) provided that subject confidentiality is maintained in agreement with HIPAA regulations.
- 12.4 It will be the monitor's responsibility to inspect the CRFs at regular intervals throughout the study, to verify the adherence to the CIP and the completeness, consistency and accuracy of the data being entered on them.
- 12.5 During each visit, the monitor will also verify presence of informed consent, adherence to the inclusion/exclusion criteria, and documentation of SAEs/SADEs and protocol deviations/violations, and check CRF against source documentation.

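### The SAE and SADE definitions in section 9.1 omit prolongation of an existing hospital stay, and the SADE list also lacks the SAE list's intervention criterion

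*Combined protocol and SAP*

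**What the plan says.** Section 9.1 defines an SAE by its outcome. The list opens "a serious adverse event is an adverse event that results in death, inpatient", continues "hospitalization, severe or permanent disability, a life threatening illness or injury, fetal distress, fetal death, a", and closes with "congenital abnormality, a birth defect, or medical or surgical intervention to prevent permanent impairment to body" or structure. The SADE definition is shorter: "a serious adverse device effect is an adverse device effect that results in death, inpatient hospitalization, severe or permanent disability or is life threatening". An adverse event in general is broad: "an adverse event is any untoward medical occurrence in a subject which need not be related to the device under investigation".

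Section 9.3 attaches consequences to these labels. "Both Serious Adverse Events and Unanticipated Adverse Device Effects must be reported to the Sponsor within 48 hours". Every other adverse event is due to the sponsor within 5 business days. SAEs and UADEs also go to the IRB; no IRB route is stated for other events. Section 12.5 has the monitor verify "documentation of SAEs/SADEs and protocol deviations/violations".

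Section 5.2 restricts enrolment to ASA III or IV patients, each "Scheduled for an elective surgical procedure requiring endotracheal intubation" and an arterial catheter placed before induction. Section 6.2 names thermal burn as a sensor risk, and section 9.2 adds mild allergic reaction, discomfort, redness and skin irritation.

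**The concern.** The hospitalization criterion asks whether the event caused an admission. In a patient already admitted, or about to be admitted as planned, an adverse event cannot cause that admission. What it can do is lengthen it, and neither definition covers that. For such patients the criterion reaches little beyond readmission.

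Seriousness decides both how fast the sponsor hears of an event and whether the IRB has a stated route to hear of it. A complication that only extends the stay would therefore take the slower path, in a population where a longer stay is a natural form for a complication to take.

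The second discrepancy is between the two lists. A reader would expect a serious device effect to be an adverse device effect that is serious by the plan's own standard. The SADE list drops a criterion that the SAE list uses, so the two labels can disagree on the same event.

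**Working it through.** The plan gives no figure on this point, so the check is a comparison of the lists followed by a trace of cases through the reporting rules.

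**Step 1. The lists side by side.**

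| Criterion | SAE (9.1) | SADE (9.1) | Outcomes named for reports (9.3) |
|---|---|---|---|
| Death | yes | yes | yes |
| Inpatient hospitalization | yes | yes | yes |
| Longer existing stay | no | no | no |
| Severe or permanent disability | yes | yes | yes |
| Life threatening | yes | yes | yes |
| Intervention against permanent impairment | yes | no | no |
| Fetal or congenital outcome | yes | no | no |

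The last row matters little, because section 5.3 excludes pregnancy. The list in 9.3 is expressly not exhaustive, but the outcomes it names are those of the shorter SADE list.

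**Step 2. Cases traced through 9.1 and 9.3.**

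| Case | Labels | Sponsor deadline | IRB |
|---|---|---|---|
| A. Admitted subject; not device-associated; only consequence is a longer stay | AE | 5 business days | none stated |
| B. As A, but unanticipated and device-associated | AE and ADE; UADE if judged serious | 48 hours if UADE, otherwise 5 business days | yes if UADE |
| C. Sensor burn treated to prevent permanent impairment, no other serious outcome | AE, ADE, SAE; not SADE | 48 hours | yes |
| D. Fatal, life-threatening or disabling event | SAE | 48 hours | yes |
| E. Same-day patient whom the event causes to be admitted | SAE | 48 hours | yes |

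Case A is the gap. Case B is uncertain: the UADE definition uses the word serious without tying it to the SAE list, so it could be read either way. Case C is an SAE because an untoward device effect is also an adverse event and the SAE list has the intervention criterion. Case E shows that the criterion works as written for anyone not already admitted or due to be.

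**Step 3. Size of the delay in case A.** Five business days counted from a weekday cross one weekend: 5 + 2 = 7 calendar days, assuming no public holiday. Against 48 hours, or 2 days, the deadline moves by up to 7 − 2 = 5 calendar days.

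**Step 4. Where the SADE label is used.** Section 9.3 does not name SADE as a trigger for any report. After 9.1 the term returns only in the monitoring check in 12.5. The published statistical plan in section 8 describes no safety analysis and hence no planned SADE count.

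**The case against.** The strongest reply is that little is lost. All adverse events must be recorded and reported promptly to the sponsor, with 5 business days only the outer limit. Section 14 has the principal investigator evaluate every adverse event and judge whether the study is safe to continue. The UADE definition could catch an unanticipated device effect that prolongs a stay. Nothing forbids an extra IRB report. Study exposure is a noninvasive sensor and a few blood samples around induction. A site might also read hospitalization as including prolongation.

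This limits the size of the point but does not close the gap. Prompt reporting carries no shorter clock than the 5-day limit. The UADE route is confined to unanticipated, device-associated effects, so case A stays outside it. Reliance on a generous reading leaves classification to each assessor.

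The objection is right that inpatient status is an assumption. Section 5.2 describes the procedure and the arterial catheter, not admission, and being in an operating room is not the same as being an inpatient.

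A reader might also infer more than the text supports:

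- *Serious events in general are filed as non-serious.* They are not; cases C, D and E are all captured.
- *The SADE gap slows reporting.* It does not; case C is an SAE and SADE triggers nothing in 9.3.
- *All 22 to 100 subjects are affected.* That is the enrolment range, not a count of misfiled events.
- *Burn is the only device risk named.* Section 9.2 names others.
- *The definitions depart from the cited ISO standard or federal regulation.* Neither text is reproduced in the documents, so no such conclusion is drawn.

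**Conclusion.** The point holds in a limited form. As written, an event whose only serious consequence is a longer existing stay meets no SAE or SADE criterion. It is due to the sponsor within 5 business days instead of 48 hours, up to 5 calendar days later, and has no stated IRB report unless it qualifies as a UADE. This rests on the assumption that most subjects are admitted or have a planned admission. The documents give no rate for such events, so no expected number can be stated.

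The SADE omission is an internal inconsistency with a smaller effect. A device effect needing intervention to prevent permanent impairment is an SAE and an ADE but loses the SADE label that the monitor looks for. Any tally of SADEs would run low, though none is planned in the published text, and the event would still be checked under its SAE label. The definitions should be corrected because the change is small and concerns timely safety reporting.

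**What to change.** In section 9.1:

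- Extend the hospitalization criterion in both definitions to cover *inpatient hospitalization or prolongation of existing hospitalization*.
- State that the planned surgical admission is not itself an SAE.
- Define a SADE as an adverse device effect that meets any SAE criterion, which brings in the intervention criterion and keeps the two lists in step.

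In section 9.3, align the named outcomes with the revised list, and make the matching change on the Adverse Event Report Form.

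The cost is a few words of protocol text and a form edit, made through the amendment and IRB approval route in section 13.4. The small downside is that a few more events will fall under the 48-hour and IRB reporting rules. No study procedure or analysis changes.

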#### 9.2 Anticipated Adverse Events:

Mild allergic reaction to sensor material and adhesives.

Discomfort, redness or skin irritation.

# 9.3 Adverse Event Reporting:

- All Adverse Events, both Anticipated and Unanticipated, must be recorded in the within the CRF and in the Adverse Event Report Form.
- All Adverse Events must be promptly reported to the Sponsor.
- All Unanticipated Adverse Device Effects will be also reported to both the Sponsor and the IRB.
- Both Serious Adverse Events and Unanticipated Adverse Device Effects must be reported to the Sponsor within 48 hours. All other Adverse Events should be reported to the Sponsor within 5 business days.
- All Serious Adverse Events will be also reported to the IRB per IRB reporting requirements. These reports may include, but will not be limited to: date of onset; brief description of the events; their treatment; whether they resulted in death, inpatient hospitalization, severe or permanent disability or were life threatening; their relationship to the study device; and resolution.

#### 9.4 Deviations from the study protocol

Deviations from the protocol must receive both Sponsor and the investigator's IRB approval before they are initiated with the exception that under emergency circumstances, deviations from the CIP to protect the rights, safety and well-being of human subjects may proceed without prior approval of the sponsor or the EC. Any protocol deviations initiated without Sponsor and the investigator's IRB approval that may affect the scientific soundness of the study, or affect the rights, safety, or welfare of study subjects, must be documented and reported to the Sponsor and to the investigator's IRB as soon as a possible, but no later than 5 working days of the protocol deviation. If protocol deviations continue to occur frequently at a study site, a corrective and preventive action (CAPA) may be opened by the Sponsor.

# 9.5 Withdrawal of IRB approval

An investigator shall report to the sponsor a withdrawal of approval by the investigator's reviewing IRB as soon as a possible, but no later than 5 working days of the IRB notification of withdrawal of approval.

# 10 VULNERABLE POPULATIONS

### 10.1 **Definition**

10.1.1 Vulnerable populations are defined as disadvantaged sub-segment of the community requiring utmost care, special considerations and protections in research. This study will recruit subjects from the following: economically disadvantaged or unemployed, educationally disadvantaged, and limited English skills and/or Non-US citizens.

# 10.2 Protection of vulnerable subjects

- There is no compensation provided for economically disadvantaged subjects to eliminate possibility of undue influence due to financial incentive.
- Educationally disadvantaged subjects will be provided ample time to ask questions and comprehend information.

 Medical care will be provided to these subjects if they are injured as a direct result of participating in this research study. The cost of treatment for any research related injury will be covered by Masimo.

### 10.3 **Responsible Parties**

- The IRB will review research with vulnerable populations and evaluate consent, level of risk, coercion, and the
  reason for choosing this particular subject population. The IRB will be responsible for determining what practices
  will include continuing review for compliance while monitoring these studies.
- The Investigator holds the ultimate responsibility for protecting the rights, safety, and welfare of research subjects by ensuring that all regulations and proper documentation of consent is handled in a compliant and timely manner.

#### 11 DATA MANAGEMENT

#### 11.1 Confidentiality of Records

Information about the patients will be kept confidential. The data will be stored on a password protected database on a secure server, accessible only to the Investigators. Study data that will be released to Masimo and other regulatory authorities will be de-identified and will only pertain to study data collection, demographics, finger location of the sensor, and the recordings from the pulse oximeter.

#### 11.2 Source Documents

Source data is all information, original records of clinical findings, observations, or other activities in a clinical trial necessary for the reconstruction and evaluation of the trial. Source data are contained in source documents. Examples of these original documents and data records include: hospital records, clinical and office charts, laboratory notes, memoranda, recorded data from automated instruments, and copies or transcriptions certified after verification as being accurate and complete. For this study, the case report forms may also be used as source worksheets.

# 11.3 Case Report Forms

The Site shall capture study data in the CRFs for each subject enrolled. The CRFs will be completed and initial and dated by the PI or delegated personnel. This also applies to those subjects who fail to complete the study. If a subject withdraws from the study, the reason must be noted on the CRF. Case report forms are to be completed on an ongoing basis. CRF entries and corrections will only be performed by study site staff, authorized by the investigator. Entries and corrections to the CRF will be made following Good Documentation Practices.

The CRF will include the following information, including but not limited to: inclusion/exclusion criteria, whether patient consent obtained before start of study, demographic information, device readings, and if occurrence of any adverse event, protocol deviation, and device deficiencies, etc. The CRFs will be signed by the PI to attest that the data is complete and accurate and forward a copy to Masimo.

CRF entries will be verified by study monitor and any errors or inconsistencies will be queried to the site on an ongoing basis. Any changes will be made directly on the paper CRFs and re-verified. Query resolution will be assessed and confirmed by study monitor during site visit. The monitor or study manager will collect original completed and signed CRFs at the end of the study. A copy of the completed and signed CRFs will remain on site

# 11.4 Data Transfer and Storage

The information will be stored in a password protected electronic database at the study site. Device data along with an electronic copy of the CRF will periodically be securely uploaded to sponsor via secure FTP portal. Only authorized sponsor personnel will have access to the transferred data, and will move it to a secure and backed-up drive at Masimo. CRFs will be checked for accuracy and completeness of data. If there are inconsistent or missing data points, a data query list will be generated and submitted to the PI or designee, who shall both follow GDP practices for data correction by striking through the old entry, adding in new entry with initial and date, and resend to Masimo the corrected CRF. Once all queries

have been resolved, Masimo engineers are notified that data is ready for analysis. To ensure data integrity, Masimo engineers will only have read access to study data, therefore are unable to unintentionally tamper with the original data files.

### 11.5 Record Retention

All study information, including but not limited to study correspondence, study logs, device accountability records, consent forms, subject records, and copies of CRFs should be maintained in the Investigator site files.

Study records shall be retained during the study and for a minimum of two years after date of study closure or date when records are not required to support 510(k) clearance. The Institution's own retention policies and regulations may apply in addition to the minimal requirement.

The Sponsor is responsible for verifying study data, retaining records, analyzing data, and authoring study reports.

#### 12 MONITORING PLAN

- 12.1 As the sponsor of this clinical investigation, Masimo Corporation is required by 21 CFR Part 812, of the Food and Drug Administration regulations to monitor and oversee the progress of the investigation. The monitor(s) assigned by Masimo Corporation to this task will be a direct employee from the Clinical Research department trained on departmental SOPs on conduct and monitoring of sponsored studies.
- 12.2 In accordance with good clinical practices guidelines, there will be at least three scheduled monitoring visits to ensure overall regulatory compliance of the study:
  - An initiation visit, prior to any subject enrollment to confirm site readiness, and to document training on the study protocol and procedures, and use of equipment.
  - At least one monitoring visit during enrollment, when about 10-15% done and/or every year
  - A final close out visit after the last patient had finished the study.
- 12.3 The monitor will contact and visit the investigator and will be allowed, on request, to have access to all source documents needed to verify the entries in the CRFs and other GCP-related documents (IRB approvals, IRB correspondences, and ICFs) provided that subject confidentiality is maintained in agreement with HIPAA regulations.
- 12.4 It will be the monitor's responsibility to inspect the CRFs at regular intervals throughout the study, to verify the adherence to the CIP and the completeness, consistency and accuracy of the data being entered on them.
- 12.5 During each visit, the monitor will also verify presence of informed consent, adherence to the inclusion/exclusion criteria, and documentation of SAEs/SADEs and protocol deviations/violations, and check CRF against source documentation.
- 12.6 After each visit, the monitor will provide a monitoring report to the investigator within 4 weeks of visit completion. The monitoring report will detail findings and open action items observed during the visit. It is the responsibility of the Principal Investigator and Study Coordinator(s) to respond to the findings of the monitoring report, and complete any open action items as soon as possible but no later than 60 days of receiving the monitoring report. Any open action items not completed within the time allowed may be sufficient grounds for study site suspension or termination; it will be up to the sponsor to determine whether any incomplete action items are sufficient grounds for suspension or termination. See Section 13 for details on suspension and termination.
- 12.7 Depending on the quality of the data and/or changes to factors affecting patient safety, additional monitoring visits may be necessary according at the sponsor's discretion.

### 13 ADMINISTRATIVE ASPECTS

# 13.1 Protection of Human Subjects

Per 21 CRF 50, written consent must be obtained from each subject or from their legal guardian prior to any study procedures in accordance with applicable federal, state, and study site regulations. The Investigator must keep a copy of the signed consent form in each subject's record and provide a copy to the subject as well. The Investigator shall not allow a subject to participate in a study or sign consent prior to IRB approval.

Prior to the start of data collection or subject enrollment, the Investigator must provide documentation of IRB approval of the study protocol and a copy of the approved informed consent form (21 CFR 50).

All subjects will be monitored closely throughout the study. The following measures will be taken to ensure the privacy of subjects:

- A code (unique identification) number for each subject will be kept on file.
- Only their correspondence identification number will identify subjects.
- Access to the documents and data will only be made to the Investigators and study staff in the study.
- The confidentiality of these documents will be protected to the extent provided by the law.

